8.3 Sampling time frame

8.3.1 Data collection window

8.3.1.1 Start date

The study launches on 1st December 2023

8.3.1.2 End date

Final submission of data will be at the discretion of the PMT, with a provisional deadline of 1st March 2024, with scope to extend to promote data completeness.

8.4 Consent

This audit will report the treatment recommendations and outcomes of management that have already taken place. There will be no impact on the management of patients as a result of inclusion in the study. All data will be anonymised, and no patients will be identifiable in subsequent reports, presentations or publications. As such, consent from individual patients will not be required.

8.5 Anonymisation of patients

The PMT will neither request nor be provided names, addresses, date of birth, race, NHS numbers, medical record numbers (MRN) or identifiable information for any patients.

Reporting and analysis will not identify individual cases in any subsequent reports, presentations or publications.

Data flow will be one-way, from the Data Disclosure to the Data Receiver (PMT). There will be no traceability from the PMT's database to local records.

If any identifiable data is received, the files will be deleted and the site will be informed.

8.6 Dataset

The full dataset is delineated in the study Excel Data Tool. This tool will collect data in the following areas:

- Demographics and referral details: demographics; smoking status; alcohol status; ECOG performance status; source of referral
- MDT details: unit type (tertiary referral or district general); frequency of MDT; platform; same-day clinic; specialties present; allied healthcare professionals
- Cancer pathway dates: date of referral; date of first specialist clinic; date of biopsy; date of MDT outcome; date patient was informed of diagnosis; date treatment commenced; FDS
- Diagnostic biopsies: date of biopsy(s); subsite(s); anaesthesia; location (clinic or operating theatre)
- Imaging for diagnosis: modality, body site
- Diagnosis: subsite; clinical T stage; clinical N stage; clinical M stage; TNM 8; new or recurrence; p16 and HPV status; EBV status; PDL-1 status; presence of clinical ENE; presence of synchronous head and neck tumour
- Presence of synchronous HNSCC: subsite; clinical T stage; TNM 8; new or recurrence; p16 and HPV status; EBV status; PDL-1 status
- **Treatment:** modality of treatment (including surgical and/or oncological technique, timings or doses); treatment intent
- **Recurrence:** recurrent or residual disease; nature of recurrence (local, regional or distant); timing of recurrence after completion of treatment; treatment of recurrence
- Surveillance: timing of post-treatment surveillance imaging; modality
- Follow-up: time to last follow-up and/or death; cause of death

8.6.1 Classification of residual and recurrent disease

The following time frames will be used to classify tumours treated after management of the primary disease:

<12 months: Residual disease
 ≥12 months, <5 years: Recurrent disease

• <5 years >3cm from primary: New primary disease, separate site

• ≥5 years New primary disease

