5.3 Secondary Objectives

- 1. To gain an understanding of the variation in HN MDT recommendations
- 2. To evaluate the 2-year overall, disease-specific and disease-free survival outcomes, and recurrence rates of head and neck cancers
- 3. To audit UK-wide HNSCC pathways and their compliance with cancer waiting targets, including identifying delays and potential areas for improvement
 - a. 28 days 'Faster Diagnosis Standard' (FDS) for primary HNSCC
 - b. 31 days from the referral to decision-to-treat
 - c. 62 days from referral to the commencement of treatment (31 days for recurrent HNSCC)
- 4. To examine the use of local anaesthetic biopsy for histological diagnosis and its impact on pathway timings
- 5. To assess the HN MDT workforce against national guidelines

6 Study design and setting

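### The residual/recurrent/new-primary categories in Section 8.6.1 overlap, conflict with the recurrence field in Section 8.6, and leave the 2-year recurrence numerator undefined

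*Protocol*

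**What the plan says.** Protocol Section 8.6.1 introduces its scheme with "The following time frames will be used to classify tumours treated after management of the primary disease" and gives four rules:

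- "<12 months: Residual disease"
- "≥12 months, <5 years: Recurrent disease"
- "<5 years >3cm from primary: New primary disease, separate site"
- "≥5 years New primary disease"

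Section 8.6 lists what is collected under the single heading of recurrence: "recurrent or residual disease; nature of recurrence (local, regional or distant); timing of recurrence after completion of treatment; treatment of recurrence". The secondary objective that uses these data (Section 5.3) is "To evaluate the 2-year overall, disease-specific and disease-free survival outcomes, and recurrence rates of head and neck cancers". Follow-up is 2 years.

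The new/recurrent distinction is used in three other places. Section 7.1 admits new or recurrent disease. Section 10.3 plans primary and recurrent subgroups. Section 5.3 applies the Faster Diagnosis Standard to primary disease and gives recurrent disease a 31-day rather than a 62-day limit to treatment.

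**The concern.** A classification applied by many sites has to give each tumour one label. This one can give two, and it does not say which wins. Its distance rule also sits badly with a data field that treats regional and distant disease as kinds of recurrence. Finally, it separates residual from recurrent disease by elapsed time alone, so relapse at 9 months after documented clearance carries the same label as disease that never cleared.

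Two things are at stake. The first is the 2-year recurrence rate and disease-free survival, if the labels decide what counts as an event. The second is the index cohort. The 5-year category cannot arise within a 2-year follow-up, so the scheme evidently also classifies tumours at entry, where the label bears on eligibility, subgroup and waiting-time standard.

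**Working it through.** The protocol states no recurrence rate, event count or sample size, so there is no figure to reproduce. The main check is logical.

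**Step 1: apply the four rules as written.**

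| Time | Distance from primary | Labels that apply |
|---|---|---|
| 6 months | 1 cm | Residual |
| 6 months | 10 cm | Residual and new primary |
| 18 months | 1 cm | Recurrent |
| 18 months | 10 cm | Recurrent and new primary |
| 61 months | either | New primary |

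Within a 2-year follow-up, only a tumour at 12 to 24 months and within 3 cm is unambiguously recurrent.

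**Step 2: try each order of precedence.** The first two bands together cover all times under 5 years. If time prevails, the distance rule never operates. If distance prevails, a distant metastasis at 18 months becomes a new primary. So does most regional relapse, on the assumption that neck nodes usually lie more than 3 cm from the primary. Section 8.6 codes the same events as regional or distant recurrence. Neither order makes the two sections agree.

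**Step 3: index tumours.** Disease re-treated before 12 months is residual. That is neither new nor recurrent under Section 7.1, falls in neither subgroup of Section 10.3, and has no assigned standard in Section 5.3.

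**Step 4: illustrate the effect of a numerator restricted to the recurrent label.** All inputs here are assumptions. Let R be the 2-year relapse risk, with F(t) = 1 − exp(−H(t/24)^k) and H = −ln(1 − R).

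For R = 30% and constant hazard (k = 1):

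- Year-1 risk = 1 − √0.70 = 16.3%.
- Share of events in year 1 = 16.3/30 = 54%.
- Months 12 to 24 = 30 − 16.3 = 13.7%.

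| Assumed R | Months 12–24, k = 1 | k = 0.7 | k = 0.5 |
|---|---|---|---|
| 20% | 9.4% | 7.2% | 5.4% |
| 30% | 13.7% | 10.3% | 7.7% |
| 40% | 17.5% | 13.0% | 9.7% |

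If the distance rule also removed events, and 40–80% of them lay within 3 cm (assumed), the 30% row would fall to between 7.7% × 0.4 = 3.1% and 13.7% × 0.8 = 10.9%.

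**Step 5: time origin.** Section 8.6 times recurrence from completion of treatment. The protocol does not fix the origin of the 12-month band or of the 2 years. If the 12 months run from treatment completion and the 2 years from the MDT decision, the window for a recurrent label is 24 − (12 + d) months, where d is the time from MDT decision to end of treatment. For assumed d of 2, 4 or 6 months it is 10, 8 or 6 months.

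**The case against.** A reader might infer that the reported recurrence rate will count only local events in months 12 to 24, and that disease-free survival will miss most events. The documents do not support that. No section says residual disease is left out of either outcome. Section 8.6 places residual and recurrent disease under one heading and collects nature and timing for them, so a combined rate can be built. Deaths and follow-up time are recorded separately. The event definition may also stand in an analysis plan that is not shown. 'Only local' is inexact too, because a nearby node can lie within 3 cm. All of this stands.

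It can also be said that the words 'separate site' naturally describe a second tumour, and that the regional/distant field shows the authors regard nodal and distant disease as recurrence. That is a plausible intention, but the rule carries no such exception. The Excel Data Tool might guide sites better; it is not shown.

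A time cut-off has a real merit in retrospective work: it is reproducible, whereas documented clearance depends on the quality of the notes. That argues against making disease status compulsory as the basis of the classification. It does not excuse the overlap.

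Later repair has limits. The recurrence item in Section 8.6 names only recurrent or residual disease, so an event labelled new primary has no evident place there, and neither distance nor disease-free status is listed. Data flow is one-way without traceability to local records (Section 8.5). The completeness check in Section 9.1.3 would not flag a wrong label that had been validly entered.

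**Conclusion.** The fault holds on the wording of the protocol. The categories are not mutually exclusive, they conflict with the recurrence field in Section 8.6, and they leave index disease re-treated before 12 months without a class for eligibility, subgroup and waiting-time standard. These conclusions need no numerical assumption.

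The effect on the 2-year recurrence rate is conditional. If only tumours labelled recurrent were counted, all year-1 events would be lost. If the distance rule also prevailed, distant and most regional events would be lost as well. The protocol does not say which labels count, and the size cannot be taken from it. The 13.7% against an assumed 30% is an illustration, not a forecast.

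This is a should-fix. It affects secondary objectives and a planned subgroup, while the primary objectives concern MDT decisions and guideline adherence.

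**What to change.** - Rewrite Section 8.6.1 as mutually exclusive categories with a stated order.
- Apply the 3 cm rule only to a separate second mucosal tumour, never to nodal or distant disease, so that Sections 8.6 and 8.6.1 agree.
- For the 2-year recurrence rate and disease-free survival, count residual and recurrent disease together as events from a stated time origin, and report each separately.
- State how index disease classed as residual is handled for eligibility (7.1), the primary/recurrent subgroup (10.3) and the waiting-time standard (5.3).
- Optionally, add a documented disease-free field (yes/no, with date) to separate persistence from early relapse.

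The first four cost a rewrite of four bullets, a few sentences on events and index disease, and a matching drop-down in the Excel Data Tool. They are cheapest before sites enter data. The optional field costs extra abstraction for each re-treated patient, from notes of variable quality.

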8.7 Data collection

Anonymised data will be locally entered into the Excel Data Tool spreadsheet in accordance with local governance guidelines. This uses restricted data fields and data validation to improve data completeness and homogeneity. The PMT will securely and confidentially combine datasets from each centre for the pooled analysis.

Additionally, each site lead will be requested to complete the 'Head and Neck MDT Snapshot Survey' that assesses the participating unit's Head and Neck MDT workforce and resource availability.

8.8 Anticipated numbers/workload

Activity	Cohort	Anticipated numbers for mid-large MDT discussing 10-20 patients / week and diagnosing 200 SCC /yr
Initial identification	Patients discussed at MDT	- up to 200 / 3-month period / unit
Eligibility criteria	New or recurrent histologically confirmed HNSCC	- up to 50 / 3-month period / unit
Data collection	Documented MDT outcome between 1st September, 2021 and 30th November, 2021	- up to 50 / 3-month period / unit
	2 years of follow-up date available	- up to 50 / 3-month period / unit

9 Data Management

9.1 Data collection tools and source document identification

9.1.1 Source documents

Source documents will vary by participating site. An Excel Data Tool will be used to collate study data. No new data will be generated for the patient record as a result of this study.

9.1.2 Excel Data Tool

Data will be read from source documentation (e.g. Electronic Patient Record) and entered onto a standardised Excel Data Tool, supplied to the participating sites by the PMT. This tool has restricted data fields and data validation to improve data completeness and homogeneity. The completed Excel Data Tool allows data to be anonymised prior to secure submission to the PMT. The tool will be available to download from the project website.

9.1.3 Missing data

The PMT will check the submitted data for completeness and integrity. If necessary, the PMT will give feedback to the local team where any data fields are inadequate. The submitting team will be asked to provide the missing data where possible. If data is not available, the data point will be treated as null, and that record will be excluded from any subsequent relevant analysis where necessary.

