10.4 Analysis exclusion criteria

Patients for whom 2-year follow-up data is unavailable will not be included in the subsequent 2-year follow-up analysis.

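### The missing-data rule, applied to an unavailable cause of death, removes only patients who died from 2-year disease-specific survival and so probably overstates it

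*Protocol*

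**What the plan says.** Protocol section 5.3 makes disease-specific survival a secondary outcome: "To evaluate the 2-year overall, disease-specific and disease-free survival outcomes, and recurrence rates of head and neck cancers". Section 8.6 lists the follow-up items that it needs: "time to last follow-up and/or death; cause of death".

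Section 9.1.2 describes where the data come from: "Data will be read from source documentation (e.g. Electronic Patient Record", with the electronic record given as an example. Section 8.5 rules out later look-up by the project team: "There will be no traceability from the PMT's database to local records".

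Section 9.1.3 has two steps. The first is a query to the site: "The submitting team will be asked to provide the missing data where possible". The second applies when that query fails: "If data is not available, the data point will be treated as null, and that record will be excluded from any subsequent relevant analysis where" this is needed.

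Section 10.4 adds a separate exclusion: "Patients for whom 2-year follow-up data is unavailable will not be included in the subsequent 2-year follow-up analysis". Section 10.5 names the Kaplan-Meier method, the log-rank test and the Cox model, and promises sensitivity analyses without describing them. The protocol gives no separate handling for a death of unknown cause.

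**The concern.** Excluding records with a missing item is often tolerable when missingness is unrelated to the outcome. That cannot be so for this item. A survivor has no cause of death to lack, so every record that the rule removes for this reason belongs to someone who died. Selection then depends on the outcome, and the estimate is biased even if cause is missing completely at random among deaths.

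These patients have known vital status and lack only the cause. Overall survival would keep their deaths and disease-specific survival would drop them, so the two figures would rest on different patients. Subgroup comparisons of disease-specific survival could also be distorted if cause of death is recorded less often in one group than in another.

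**Working it through.** The protocol states no survival rate, missing-cause rate or sample size, so there is no figure of its own to reproduce. The inputs below are assumptions.

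**Inputs (assumed)**
- S, 2-year overall survival: 60–80%.
- p, share of deaths due to HNSCC: 60–90%.
- m, fraction of deaths with cause unavailable: 5–30%, at first equal for HNSCC and other deaths.
- Hazards constant over 2 years; other-cause deaths censored in the Kaplan-Meier analysis.

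**Formulas**
- All causes known: DSS = S^p.
- Under the rule: the fraction m(1−S) of all patients is deleted from time 0. Overall survival among those left is S/[1−m(1−S)], so DSS = {S/[1−m(1−S)]}^p.
- Unknown-cause deaths kept and censored: DSS = S^[p(1−m)].
- Unknown-cause deaths kept and counted as HNSCC: DSS = S^[p+m(1−p)].

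**Example: S = 0.70, p = 0.75, m = 0.20**
- All causes known: 0.70^0.75 = 76.53%.
- Under the rule: 0.20 × 0.30 = 0.06 of patients deleted; (0.70/0.94)^0.75 = 80.16%, which is 3.63 points too high.
- Kept and censored: 0.70^0.60 = 80.73%.
- Kept and counted as HNSCC: 0.70^0.80 = 75.18%.

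The last two values bracket the true one. Censoring alone is no cure, because here it is as optimistic as deletion.

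**Range of the overstatement over the assumed S and p**

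| Causes missing | Smallest (S = 0.80, p = 0.60) | Largest (S = 0.60, p = 0.90) |
|---|---|---|
| 5% | 0.5 points | 1.2 points |
| 10% | 1.1 | 2.4 |
| 20% | 2.2 | 4.9 |
| 30% | 3.3 | 7.7 |

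For the 20% row: (0.80/0.96)^0.60 − 0.80^0.60 = 89.6% − 87.5%, or 2.2 points before rounding; (0.60/0.92)^0.90 − 0.60^0.90 = 68.1% − 63.1%, or 4.9 points before rounding.

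**Dependence on who has the unknown cause.** Let q be the share of unknown-cause deaths that are in fact HNSCC deaths. In the example, a step-by-step Kaplan-Meier calculation gives a bias of −0.7 points at q = 0, −0.1 at q = 0.10, +2.2 at q = 0.50, +3.6 at q = 0.75 and +5.1 at q = 1. The sign changes at q of about 12.5%. Over the assumed ranges the break-even lies at about 7–20% for Kaplan-Meier. For a crude 2-year proportion it equals the 2-year risk of HNSCC death, p(1−S), which is 12–36%.

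**The case against.** **Direction.** A reader might infer that the rule always raises disease-specific survival. It does not: if few unknown-cause deaths were from HNSCC, the bias would turn slightly negative. So low a share seems unlikely in a cohort selected for HNSCC, but the documents do not exclude it.

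**Net effect.** A reader might also infer that the reported figure is shown to be too high. Section 10.4 prevents that conclusion. If it removes survivors with short follow-up while early deaths stay in, it pushes survival down. The present point concerns one rule and not the sum of both.

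**Source of the cause.** It is tempting to say that the hospital record is the only source. Section 9.1.2 offers the electronic record as an example, section 9.1.1 lets source documents vary by site, and section 9.1.3 queries the site first. These steps reduce the number of missing causes. They do not help where no document open to the site holds the cause.

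**Wording and unseen documents.** The rule is general and leaves some discretion. The Excel Data Tool is not shown and may already have a code for unknown cause. Classifying such deaths could also be left to a statistical analysis plan. This stands in part. However, the protocol does not leave the matter open: it fixes exclusion as the default and writes no alternative. An unknown-cause code alone would not say how the death is analysed, and unspecified sensitivity analyses do not change the main estimate.

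**Importance.** The primary objectives and overall survival are untouched, and no stated threshold rests on disease-specific survival. With 5% of causes missing, the effect is about a point or less.

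**Conclusion.** The concern holds in a limited form. Applied as written to cause of death, section 9.1.3 selects on the outcome, and the likely effect is to overstate 2-year disease-specific survival. The size rests wholly on assumed rates: about 0.5–1.2 points if 5% of causes are missing and 2.2–4.9 points if 20% are, with cause missing equally often for HNSCC and other deaths. The documents give no missing-cause rate. They support neither a certain direction nor a net bias in the reported figure. What they do show is a rule that can delete only deaths from a named survival outcome, with no other handling written. That is worth correcting, though it concerns one secondary outcome.

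**What to change.** State in sections 9.1.3 and 10.4 that a patient known to have died within 2 years is not excluded from disease-specific survival because the cause is unavailable. Then:

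- Keep the patient at risk to the date of death.
- Make sure that the Excel Data Tool has a code for unknown cause, and report the number of such deaths.
- Report disease-specific survival twice: with all unknown-cause deaths counted as HNSCC deaths, and with all counted as other-cause deaths (censored at death).
- Name one of the two in advance as the main estimate. Imputing the cause is optional.

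The cost is a few sentences of text, a check of one field in the tool and one extra analysis run. The downside is a result shown as a range, 75.2% to 80.7% in the example. The repair does not remove any bias from section 10.4, which needs to be considered separately.

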5.2 Primary Objectives

- 1. To gain a large-scale understanding of the management decisions of patients with HNSCC discussed at MDT in the UK
 - a. by collecting patient demographics and HNSCC disease data
 - b. by collecting MDT recommendations
- 2. To assess this management for adherence to national guidelines

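### The missing-data rule does not separate a step not done from one not recorded, so it can bias adherence and waiting-target compliance, upwards where a blank means not done

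*Protocol*

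**What the plan says.** Section 9.1.3 has the project team check each submission and go back to the site about gaps: "The submitting team will be asked to provide the missing data where possible". For what is still unavailable, "the data point will be treated as null, and that record will be excluded from any subsequent relevant analysis", qualified as applying where needed. The exclusion is per analysis, not from the whole audit.

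The rule is general. It therefore governs the second primary objective, "To assess this management for adherence to national guidelines" (section 5.2), and the third secondary objective, "To audit UK-wide HNSCC pathways and their compliance with cancer waiting targets" (section 5.3, with limits of 28, 31 and 62 days). The waiting-time measures are built from pairs of dates listed in section 8.6, among them "date patient was informed of diagnosis; date treatment commenced; FDS". The data come from retrospective local records, and "Source documents will vary by participating site" (section 9.1.1).

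Section 9.1.3 draws no line between a step that did not happen and one that happened but left no retrievable record. The protocol does not promise missing counts per standard or a rate on all eligible patients. The sensitivity analyses mentioned in section 10.5 stand in the survival paragraph and have no stated content.

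**The concern.** In an audit, an empty field can itself be the failure. Several items in section 8.6 exist only if something was done: an imaging modality, a surveillance scan, a treatment start date. If the step never took place there may be nothing to enter. A patient whose treatment never started has no start date, so the interval from referral to treatment cannot be computed and, under the rule, the record leaves that analysis. The cases that leave are then the unmet ones, or patients whose status against the standard needs to be shown.

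At stake is the meaning of the adherence percentages, which are a primary result. In the limiting case of a done/not-done standard where every 'not done' is left blank and excluded, reported adherence is 100% whatever the practice. Once blanks with different meanings have been merged, the pooled dataset alone cannot separate them again.

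**Working it through.** The protocol states no adherence rate, no missing-data rate and no sample size (section 10.1), so there is no figure of its own to reproduce. All the rates below are assumptions.

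**Inputs.** p = true adherence among patients to whom a standard applies; mA = share of adherent patients with the item missing; mN = share of non-adherent patients with the item missing.

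**Adherence under the 9.1.3 rule:** c = p(1 − mA) / [p(1 − mA) + (1 − p)(1 − mN)].

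This exceeds p when mN > mA, equals p when they are equal, and is below p when mN < mA.

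**Share missing:** m = p·mA + (1 − p)·mN.

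**Bounds on the full denominator:** the lower bound counts every missing item as not met, c(1 − m) = p(1 − mA). The upper bound counts every missing item as met, c(1 − m) + m = p + (1 − p)mN.

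Three cases worked through at p = 0.75:

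- mA = 5%, mN = 20%: 0.7125 / (0.7125 + 0.2000) = 78.1%
- mA = mN = 10%: 0.6750 / (0.6750 + 0.2250) = 75.0%
- mA = 20%, mN = 5%: 0.6000 / (0.6000 + 0.2375) = 71.6%

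| mA | mN | Missing overall | Rate under 9.1.3 | Error (points) | Worst to best bounds |
|---|---|---|---|---|---|
| 10% | 10% | 10.00% | 75.0% | 0 | 67.5% to 77.5% |
| 5% | 20% | 8.75% | 78.1% | +3.1 | 71.25% to 80.0% |
| 5% | 30% | 11.25% | 80.3% | +5.3 | 71.25% to 82.5% |
| 0% | 50% | 12.50% | 85.7% | +10.7 | 75.0% to 87.5% |
| 20% | 5% | 16.25% | 71.6% | −3.4 | 60.0% to 76.25% |
| 20% | 0% | 15.00% | 70.6% | −4.4 | 60.0% to 75.0% |

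Over the same pairs of mA and mN, the error runs from −5.5 to +15.0 points when p = 60%, and from −2.2 to +4.7 points when p = 90%.

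Two things follow. First, the sign depends wholly on mN against mA, and the protocol gives neither. For fields left blank because the step was not done, the field itself pushes mN above mA. For lost records no such ordering can be assumed. Second, the bounds contain the true 75% in every row. They must, because p(1 − mA) ≤ p ≤ p + (1 − p)mN.

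**The case against.** The strongest reply is that the rule is neutral as written: it removes any record lacking the item, adherent or not, and nothing in the protocol links missingness to non-adherence. That stands. A reader might infer that the rule removes non-adherent patients as such and that compliance is therefore overstated throughout. The document does not support this, and an illustration that sets missingness among adherent patients to zero would build the conclusion in.

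The Excel Data Tool is not shown. Sections 8.7 and 9.1.2 describe constrained fields with validation, so it may already offer 'not done' or 'not applicable'. A recorded 'not done' is available data and need not become null. This also stands, and would reduce the coding part of the fix to a sentence in 9.1.3. How each denominator is built may be set out in an analysis plan that is not at hand. Even so, the exclusion rule is fixed in the protocol, and it is silent on the distinction.

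Two further inferences should not be drawn. One is that comparisons between centres would reward poor record-keeping: sections 8.1 and 10.2 describe pooled analysis in which no hospital is identified, and no centre comparison of adherence is specified. The other is that the one-way data flow in section 8.5 makes site queries unanswerable. It bars tracing from the central database to local records, but does not stop a site from answering out of its own working file. Section 8.3.1.2 also allows the deadline to move so that gaps can be filled. What remains is that no query can recover a date for something that never happened.

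Finally, a blank may mean that the standard does not apply to that patient, and counting 'not documented' as not met would measure record-keeping as well as care. Both are reasons for separate codes and for bounds, not for treating every blank as a failure.

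**Conclusion.** The concern holds in a limited form. Section 9.1.3 fixes an available-case rule for the primary adherence result and the waiting targets without distinguishing 'not done' from 'not recorded or not retrievable'. Overstatement is likely where a blank means that the step did not happen; where records are simply lost, the bias may be zero or downward. At an assumed true adherence of 75%, the moderate scenarios move the reported figure by about 3 points either way (78.1% or 71.6%), and equal missingness leaves it at 75.0%. Actual size and direction cannot be settled from the protocol. The firm conclusion is that, under the rule as written, readers could not tell which situation applied to a given standard.

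**What to change.** In section 9.1.3, and in the Excel Data Tool if the options are not already there:

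- Code 'not done', 'not documented', 'not applicable' and, for treatment dates, 'treatment not started' as separate values.
- For each standard, take as denominator all patients to whom it applies. Count 'not done' as not met; 'not applicable' falls outside the denominator.
- Report the number missing per standard. Beside the available-case rate, give bounds with missing counted first as not met and then as met. With an available-case rate of 75%, for example, the bounds are 67.5% to 77.5% at 10% missing (0.75 × 0.90 = 0.675, plus 0.10) and 60% to 80% at 20% missing (0.75 × 0.80 = 0.60, plus 0.20).
- Show 'treatment not started' as its own row, and give interval compliance with and without those patients.

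The codes should be in place before sites enter data. The cost is slightly more data entry and a headline figure that may be less favourable or carry a wider range.
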